## 7. Exclusion criteria

- Absence of information on the oncologic treatment received;
- Lack of general or specific consent for this study

## 8. Scientific methods and sample size

The statistical method to define a required sample size for an AI-based algorithm development is not clearly defined at this point. Our target sample size ( $n=200$ ) is based on several approaches of calculations. Firstly, based on our experience with similar type of studies. For example, an AI algorithm predicting the response to immunotherapy based on digital pathology was developed based on a set of 76 cases in total. An alternative approach is based on our goal of a classifier with final ROC-AUC value of 0.75 or above with the null hypothesis value to be 0.5. We are aiming for a type 1 error value of 0.05 and for a power of 90%. Approximately 20% of patients are fast progressors (PD within first year of treatment). Total sample size required based on these assumptions is 96 with 16 fast progressors and 80 responders (calculated by MedCalc). Considering our goal to produce a highly robust classifier, and considering the relative lack of

robust manners to calculate sample size, we'll aim for a sample size that is roughly 2-3 times larger than the mentioned numbers, and have set therefore our goal as n=200.

AI-based analysis of images of the training cohort will be conducted using various methods, including machine-learning and deep learning methods. The methods deemed to provide optimal separation between R and NR will be utilized further and validated on the validation cohort and lastly on the test cohort. Training/validation/test sets will be derived from the entire study samples and split about 70:15:15.

Classification of the cases to R and NR in each phase of the study, on each of the three cohorts (training, validation and test) will be examined for dependence on potential confounders by multivariate analysis. Covariates to be considered include: age, sex, BMI, smoking status, time from diagnosis of advanced disease to ALK inhibitor initiation, specific ALK inhibitor used, ALK-fusion of variant 3 or other, co-mutations, histology, method of ALK-fusion analysis, presence of brain metastasis, site of tissue analysis and site of section scanning. Each of these additional clinical/molecular parameters will be utilized if available for more than 70% of the cohort.

In addition, technical parameters such as precise fixation technique, width of sections, type of scanner and similar factors may have significant influence of the image analysis, and care will be taken not to integrate such factors into the algorithm. The generation of the classification algorithm will include at the learning phase repeated shuffling of the cases from various centers and different technical features, thus preventing biased classifications.

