## 1. Background

About 4% of NSCLC patients harbor a rearrangement of the ALK gene, producing a novel chimeric kinase that drives cancer evolution and progression. ALK inhibitors have been developed and are currently the most active agents for the treatment of such patients, with a response rate around 80% (82.9% for alectinib-treated patients on the ALEX study). Regarding long-term outcome, on the ALEX trial at five-years follow up, the median survival was not reached yet with 62.5% of the alectinib-treated patients still alive. However, a subgroup of these patients do not respond to this treatment or demonstrate only a short-term response followed by rapid progression. Specifically, in the ALEX study, the one-year event-free survival was 68.4% (95% CI 61.0% to 75.9%), meaning 31.6% had progressed or died on alectinib within a year. In the CROWN study, 78% (95% confidence interval [CI], 70 to 84) were alive and without disease progression at 12 months in the lorlatinib group; thus, with this treatment only 22% had progressed or died within the first year. These results are numerically better with lorlatinib vs alectinib. However, the confidence intervals overlap and in general cross-trial comparisons are not valid. Therefore, and especially considering the very good long-term survival data for alectinib, lorlatinib is considered more relevant for later-line treatments.

No tools are currently available to predict the response to ALK inhibitors and to identify the sub-group of patients that will progress rapidly. Mechanisms of resistance are multiple, consisting of pathway-dependent ALK mutations or amplifications, or off-target activation of bypass growth-factor signaling pathways. Additional mechanisms of resistance include epithelial-to-mesenchymal transition (EMT), SCLC transformation, activation of drug-efflux mechanisms; in a large proportion of cases, the mechanism of resistance remains elusive.

Prediction of resistance is limited currently. Variant 3a is recognized as one with higher rate of resistance development, mostly by ALK mutations. In general, resistance to advanced-generation ALK inhibitors is more commonly accompanied by ALK mutations. Importantly, identification of ALK fusion by IHC may be a less reliable method than FISH or NGS.

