### 5. Study conduct

- 1) Participating centers will secure an ethics and administrative approval for retrospective collection of clinical data, and provision of a single H&E stained FFPE section. ALK positive patients will be identified from the working database of each center, data will be collected locally, deidentified and collected centrally. Data collected will include demographics (age, sex, smoking status, co-morbidities, BMI), tumor characteristics (histology, ALK testing utilized, specific test results, co-mutations if known, ALK fusion partner and variants, brain metastasis) and treatment (ALK inhibitor utilized, date initiated, dose reductions, treatment breaks, date of documented progression, date of death or last follow-up). We will aim to include only or mostly patients with NGS results available, to allow for robust and valid identification of the ALK-fusion, as well as the variant type and co-mutations, all proven potential confounders. Next, the required H&E slides will be stripped from identifying details, coded. The scanning of pathology slides will be performed; alternatively, the option of sending the image files instead of the slides themselves is available.
- 2) Image analysis and AI development will be carried out at the Sheba Medical Center, in-house development. The clinical data will be analyzed, tagging study samples as belonging to a responder (R), vs. a non-responder (NR). For the purpose of this study, a NR will be defined as a patient that has progressed or died on an ALK inhibitor treatment within the first year of treatment. Considering most patients would be on alectinib as first-line ALK inhibitor, we expect about 32% of the samples to belong to the NR group. A 30-

70 to 40-60 split between two classes is a reasonable split for the development of a classifier.

The study cases will be randomly split to three: a training cohort, a validation cohort and a test cohort. The cohorts will be stratified by the response to treatment (i.e. equal proportion of R vs. NR cases in each cohort). Next, scanned images will be processed and analyzed. Slides analysis would be done using python using the pytorch packages. Further statistical analysis will be done with R statistical programming.

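### Section 8's sample size of 96 (16 + 80) implies 16.7% fast progressors, not the stated 20%; at 20% the same calculation gives 85, and section 5 expects 32%

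*Protocol*

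**What the plan says.** Section 8 (Scientific methods and sample size) supports n=200 with two figures: an earlier study of 76 cases, and a formal calculation. The inputs to the calculation are "our goal of a classifier with final ROC-AUC value of 0.75 or above with the null hypothesis value to be 0.5", a type 1 error of 0.05, power of 90%, and this prevalence: "Approximately 20% of patients are fast progressors (PD within first year of treatment". The result is "Total sample size required based on these assumptions is 96 with 16 fast progressors and 80 responders (calculated by MedCalc". The protocol then decides to "aim for a sample size that is roughly 2-3 times larger than the mentioned numbers" and sets n=200.

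Section 5 (Study conduct) defines the outcome: "a NR will be defined as a patient that has progressed or died on an ALK inhibitor treatment within the first year of treatment". Because most patients should be on alectinib, it says "we expect about 32% of the samples to belong to the NR group".

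Section 1 (Background) gives the source rates. For alectinib it reports an event-free rate of 68.4% at one year, "meaning 31.6% had progressed or died on alectinib within a year". For lorlatinib, "with this treatment only 22% had progressed or died within the first year".

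**The concern.** Section 8 presents 96 as the consequence of its stated inputs, but the split printed beside it implies a different prevalence from the one assumed a sentence earlier. Either the percentage or the split is wrong, and the text does not show which.

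There is a second inconsistency. Fast progressors in section 8 and non-responders in section 5 are the same class, the one the classifier is meant to identify. Yet section 8 puts it at about 20% and mentions progression only, while section 5 puts it at about 32% and includes death.

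The 96 is the only formal calculation behind n=200. If it cannot be reproduced from its own sentence, a reader cannot tell which non-responder (NR) rate the plan rests on.

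**Working it through.** **Inputs.** From section 8: AUC 0.75 under the alternative and 0.5 under the null, alpha 0.05, power 90%, 20% fast progressors. From section 5: 32% NR. Section 8 names the software but neither the variance formula nor the sidedness. Two-sided testing and the Hanley-McNeil variance are therefore assumptions, tested in steps 2 and 5.

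**1. The split.** 16/96 = 16.7%, and 80/16 = 5. A rate of 20% gives 80/20 = 4 responders (R) per NR. Twenty per cent of 96 is 19.2, not 16.

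**2. Reproducing 96.** Let k be the R:NR ratio, Q1 = A/(2 − A) and Q2 = 2A²/(1 + A). The large-sample Hanley-McNeil form is

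V(A) = (Q1 − A²)/k + (Q2 − A²)

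n(NR) = [(1.960·√V(0.5) + 1.2816·√V(0.75)) / 0.25]²

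- At A = 0.5: Q1 − A² = Q2 − A² = 0.08333.
- At A = 0.75: Q1 − A² = 0.6 − 0.5625 = 0.0375, and Q2 − A² = 0.64286 − 0.5625 = 0.08036.

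With k = 5, V(0.5) = 0.1000 and V(0.75) = 0.08786. Then n(NR) = [(0.6198 + 0.3799)/0.25]² = 15.99, which rounds up to 16 NR + 80 R = **96**, with power 0.9002. Total and split both match the protocol. The finite-sample Hanley-McNeil form gives 17 + 85 = 102 at this ratio. The Obuchowski variance also gives 16 + 80.

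**3. At the stated 20%.** With k = 4, V(0.5) = 0.10417 and V(0.75) = 0.08973. Then n(NR) = [(0.6326 + 0.3839)/0.25]² = 16.53, which rounds up to 17 NR + 68 R = **85**. Power is 0.908 in the large-sample form and 0.905 in the finite-sample form, and both forms select 17 + 68. The excess is 96 − 85 = 11 cases, and 11/85 = 13%. Put the other way, 96 cases at 20% (19 + 77) have 93.5% to 93.7% power.

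**4. At section 5's 32%.** With k = 68/32 = 2.125, n(NR) = 18.92, giving 19 + 41 = **60** (large-sample, power 0.903). The finite-sample form gives 20 + 43 = **63** (power 0.913).

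**5. Can another convention give 96 at 20%?** At k = 4 and 90% power, the variants tried were the finite-sample form, variance under the alternative only, the Obuchowski variance and one-sided alpha. Totals ran from 65 to 85. One-sided testing does not give 96 at 5:1 either: 78 (13 + 65, large-sample) or 84 (14 + 70, finite-sample).

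**6. Effect on the multiple.**

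| NR rate used | Required total | 200 / required |
|---|---|---|
| 16.7% (the printed split) | 96 | 2.1 |
| 20% (section 8) | 85 | 2.4 |
| 32% (section 5) | 60–63 | 3.2–3.3 |

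**The case against.** The strongest objection is that nothing in the design turns on this. Section 8 says that sample-size methods for AI development are not well defined, draws on more than one approach, and sets n=200 by a loose multiple. Moving from 96 to 85 changes no decision. That is correct, and it is why the point is minor.

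The 20% is also given only as approximate, so the fault might lie in the percentage rather than the split; stating a 5:1 ratio (about 17%) would restore agreement with 96. That would repair the arithmetic. It would also leave section 8 further from section 5's 32% and without a source, since the nearest rate in section 1 is 22%. Nor does approximation explain a split that is exactly what a 5:1 input returns. One possible cause is that 20% was entered as the ratio 16/80 = 0.20, but the protocol does not say so.

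On 20% against 32%, a power input below the expected class share is conservative, and 20% lies close to the 22% reported for lorlatinib, which is an eligible drug. It is a defensible low-end value. But the protocol never calls it one, and section 5 expects most patients to be on alectinib.

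The reference to progression alone in section 8 may be shorthand, since section 5 gives the operative definition. That is fair; the wording still needs to be aligned.

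**Conclusion.** The point holds, as a minor error. The figure of 96 does not follow from the stated 20%; it follows from a 5:1 ratio, or 16.7%. At 20% the requirement is 85 (17 + 68), so the printed figure is 11 cases too high. The protocol carries three NR rates for one outcome (16.7%, 20% and 32%) and does not reconcile them.

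The mismatch between 16/96 and 20% rests on the printed numbers alone. The 85 assumes two-sided alpha and a standard single-AUC variance; the finite-sample and large-sample Hanley-McNeil forms and the Obuchowski variance all agree on it.

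The error is conservative, because 96 exceeds both 85 and 60–63, so it gives no reason to change n=200. That statement covers this error only. All the power figures above assume that every counted case enters the AUC test, whereas section 8 assigns about 15% of cases to the test cohort, or 0.15 × 200 = 30.

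**What to change.** In section 8, describe fast progressors with section 5's NR definition (progression or death within the first year) and use one planning rate.

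- **Simplest:** keep 20%, say that it is a conservative low-end value below the 32% expected in section 5, and replace 96 (16 + 80) by 85 (17 NR + 68 R). The stated multiple of roughly 2 to 3 still holds, at 2.4.
- **If 32% is preferred:** give 60 (19 + 41, large-sample form) or 63 (20 + 43, finite-sample form), name the formula, and change the multiple to about 3.2 to 3.3.

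In either case, state that alpha is two-sided if that is what was used. The sponsor should confirm the replacement figure by re-running its own software with the R:NR ratio shown. The cost is two or three sentences in section 8; n=200 stays.

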At first the whole slide image (WSI) is divided into thousands of tiles. These are examined by a convolutional neural network (CNN) to extract tile level features. We will be using Resnet, a common deep learning model used for computer vision as the CNN. The CNN will be trained with multiple instance learning (MIL) at the tile level and later the predicted scores will be aggregated for the WSI level. The final model will be conducted on the slides, to distinguish between R vs. NR. The classifier will be developed on the training cohort, modified if required following processing of the validation cohort and finally tested for efficacy on the test cohort. Cross-Validations techniques will also be used.

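### Section 8 picks methods by training-cohort separation and takes several to the test cohort, while Section 5 tests one final model; the two should be reconciled and one model locked

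*Protocol*

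**What the plan says.** Section 8 (Scientific methods and sample size) first sets the exploration: "AI-based analysis of images of the training cohort will be conducted using various methods, including machine-learning and deep learning methods". The next sentence gives the selection rule: "The methods deemed to provide optimal separation between R and NR will be utilized further and validated on the validation cohort". The same sentence ends by sending those methods to the test set as well: "validated on the validation cohort and lastly on the test cohort". It names no measure of separation and no number of methods.

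Section 5 (Study conduct) describes a single classifier built on the training cohort, "modified if required following processing of the validation cohort and finally tested for efficacy on the test cohort". It refers to one end product: "The final model will be conducted on the slides, to distinguish between R vs. NR". It adds "Cross-Validations techniques will also be used", without saying what cross-validation decides or which cases it covers.

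On size, Section 8 says "Training/validation/test sets will be derived from the entire study samples and split about 70:15:15" and "have set therefore our goal as n=200". The goal in Section 2 is one classifier with a final ROC-AUC of 0.75.

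**The concern.** The two sections differ on two points.

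- **Number of models tested.** Section 8 carries methods, in the plural, to the test cohort. Section 5 carries one final model.
- **Role of the validation cohort.** In Section 5 it is used to adjust the classifier. In Section 8 it confirms methods that have already been chosen.

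Read in order, Section 8 chooses before validation, so the criterion is separation in the training cohort. A flexible image model can separate about 140 of its own cases very well whether or not it generalises, so that criterion is a weak guide to the better method. The study's endpoint is the classifier itself, so a poor choice would matter even if it were honestly measured.

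The second risk concerns the headline figure. If several methods reach a test cohort of about 30 and nothing says which AUC is the final one, the highest could be reported as the result against 0.75.

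**Working it through.** **Inputs from the protocol.** N = 200 and a 70:15:15 split (Section 8) give 140, 30 and 30 cases. The non-responder (NR) share is 20% in Section 8 and 32% in Section 5, so a test cohort of 30 has 0.20 × 30 = 6 or 0.32 × 30 = 9.6, about 10, NR. The target AUC is 0.75 against 0.5, with alpha 0.05 and power 90%.

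**The plan's own figure.** Use the Hanley–McNeil variance, with n1 NR and n0 responders:

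Var(A) = [A(1−A) + (n1−1)(q1−A²) + (n0−1)(q2−A²)] / (n1·n0), with q1 = A/(2−A) and q2 = 2A²/(1+A).

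At the stated 16 and 80, SE is 0.0795 at A = 0.5 and 0.0745 at A = 0.75. Taking alpha as two-sided (an assumption), the power is Φ[(0.25 − 1.96 × 0.0795)/0.0745] = Φ(1.27) ≈ 0.90. The stated 96 therefore reproduces at its stated split.

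**Precision in the test cohort.** The same formula at A = 0.75 gives SE 0.124 for 6 and 24 cases, and 0.101 for 10 and 20. Chance differences between methods will be of this order.

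**Does choosing on the training cohort bias the test AUC?** No. With five methods of no merit (true AUC 0.50), the one picked on training shows a training AUC of 0.56–0.57 but a test AUC of 0.50. In a ridge-classifier simulation (140 training cases, 44 NR, 10 informative features, six penalty settings as the methods), the training-picked model had a mean 30-case test AUC of 0.545 against a true 0.552 (130 features), and 0.588 against 0.586 (200 features).

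**Does it give a poorer model?** It can. True AUC of the chosen model in that simulation:

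| Features | Picked on training | Picked by cross-validation | Loss |
|---|---|---|---|
| 20 | 0.760 | 0.771 | 0.011 |
| 130 | 0.552 | 0.662 | 0.110 |
| 200 | 0.586 | 0.642 | 0.056 |
| 500 | 0.589 | 0.598 | 0.009 |
| 1000 | 0.570 | 0.573 | 0.003 |

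The loss is clear only where the number of features is close to the number of cases. At 130 features, choosing on a 30-case validation cohort instead recovers most of it (0.642). The protocol gives no feature count, and ridge penalties only stand in for the planned network, so the table shows direction and not an expected size.

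**What if the best of several test results is quoted?** Assume three methods, each with true AUC 0.65, normally distributed scores and between-method score correlation rho (200,000 simulated test cohorts per row):

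| NR / responders | rho | Chance one method reaches 0.75 | Mean of best of three | Chance best of three reaches 0.75 |
|---|---|---|---|---|
| 6 / 24 | 0 | 0.23 | 0.76 | 0.55 |
| 6 / 24 | 0.5 | 0.23 | 0.73 | 0.45 |
| 6 / 24 | 0.8 | 0.23 | 0.70 | 0.37 |
| 10 / 20 | 0 | 0.19 | 0.74 | 0.46 |
| 10 / 20 | 0.5 | 0.19 | 0.72 | 0.38 |
| 10 / 20 | 0.8 | 0.19 | 0.69 | 0.31 |

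Hand check at rho = 0: the expected maximum of three independent normal values lies 3/(2√π) = 0.846 SD above the mean. The simulated SD of a single AUC is 0.126 (6 / 24) and 0.107 (10 / 20). This gives 0.65 + 0.846 × 0.126 = 0.757 and 0.65 + 0.846 × 0.107 = 0.741, in line with the table.

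**The case against.** The strongest reply is that Sections 5 and 8 together describe an ordinary train, tune and test design. Section 5 names one final model, lets the validation cohort modify it and plans cross-validation. Section 2 sets one classifier as the goal. Methods in the plural may mean techniques combined in one pipeline. Section 8 does not say that separation is measured by refitting to the same cases. The metric, the fold structure and the list of candidates are commonly left to a statistical analysis plan.

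Much of this stands. Missing detail of that kind is not counted here. Two stronger readings are also not supported:

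- A reader might infer that choosing methods on the training cohort inflates the final AUC. It does not, because the test cases play no part in that choice. A weak model would simply be shown to be weak.
- A reader might infer that the plan will report the best of several test results. No section says so, and testing several methods is not the same as quoting the maximum.

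What the reply does not remove is the conflict in the text. Section 8 states a rule, and on its natural reading the rule selects on training and takes more than one method to the test cohort. Section 5 describes something else, and the protocol does not say which governs.

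**Conclusion.** The point holds in limited form. Sections 5 and 8 disagree on how many models reach the test cohort and on what the validation cohort is for, and no text fixes one model or identifies the AUC to be judged against 0.75. Followed literally, Section 8 risks a poorer classifier. The size of that loss cannot be stated from the protocol: from negligible to about 0.11 in AUC in the simulation above, depending on an assumed feature count.

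Optimism in the final AUC is conditional on the best of several test results being quoted. For three methods of true AUC 0.65 it would be about 0.04 to 0.11 on average, and the chance of reaching 0.75 would rise from about 0.19–0.23 to about 0.31–0.55. The number of methods, their equal merit and their correlation are assumptions. This is a cheap improvement, not evidence that the planned result is biased.

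**What to change.** Replace the selection sentence in Section 8, and align Section 5 with it, along these lines:

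> Methods and settings will be compared on non-test data only, by cross-validation within the training cases and/or on the validation cohort. One model, with all its settings, will be locked before the test cohort is opened. Its AUC, estimated once on the test cohort, is the final ROC-AUC judged against 0.75. Any other method's result on the test cohort is exploratory.

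This keeps the tuning role that Section 5 gives the validation cohort. Grouping cross-validation folds by centre is optional and not part of the required change.

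The cost is protocol wording and a little more computing, with no extra patients or data. The reported AUC may be slightly less favourable. The wording should be settled before the test cohort is opened, since a first look at the test results cannot be undone.

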## 2. Objectives

### Hypothesis:

Identification of ALK-positive patients' subgroup at risk of rapid progression is possible at the time of diagnosis based on analysis of the H&E (Hematoxylin and Eosin) stained images of tumor sections.

**Goal of the study:** to develop an AI-driven pathologic image analysis-based classifier that can identify patients unlikely to significantly benefit from the currently utilized first-line ALK inhibitors (advanced-generation ALK inhibitors). Our goal is a classifier with final ROC-AUC value of 0.75.

**Endpoint of the study:** the development of a classifier of outcome of ALK patients, to identify patients with a high likelihood of progression on 1st-line ALK inh (2nd or 3rd generation inhibitors) within a year.

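### The 90% power in section 8 does not carry over to the 15% test cohort: about 30 cases with 6 to 10 non-responders give about 46% to 61%

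*Protocol*

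**What the plan says.** Section 2 of the protocol sets the target: "Our goal is a classifier with final ROC-AUC value of 0.75". Section 8 turns it into a sample size, with a null AUC of 0.5 and this error specification: "We are aiming for a type 1 error value of 0.05 and for a power of 90" per cent. The result is given as "Total sample size required based on these assumptions is 96 with 16 fast progressors and 80 responders (calculated by MedCalc". The sponsor then sets n = 200, some two to three times the figures mentioned, and justifies this by the wish for a robust classifier and the lack of settled sample-size methods.

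The same section divides these 200 cases: "Training/validation/test sets will be derived from the entire study samples and split about 70:15:15". Section 5 gives the cohorts their roles. The classifier is developed on the training cohort, then "modified if required following processing of the validation cohort and finally tested for efficacy on the test cohort". The split is stratified so that each cohort has the same share of non-responders (NR). That share is put at about 20% in section 8, while section 5 says "we expect about 32% of the samples to belong to the NR group". On cross-validation, section 5 says only: "Cross-Validations techniques will also be used".

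**The concern.** A sample size for testing an AUC against 0.5 counts independent cases on which a fixed classifier is evaluated. The protocol compares the resulting 96 with the whole study and then spends 70% of the study on fitting and 15% on modification. Only the remaining 15%, about 30 cases, enters the final test. That is under a third of the 96, with 6 to 10 NR instead of 16. Enlarging the total to 200 does not make up for this: at a 15% share, 96 test cases would need 96 / 0.15 = 640 in total.

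The study's only power statement would therefore not describe its only named final test. A classifier with a true AUC of 0.75 could well fail that test, and a modest classifier could appear to meet the goal. Someone reading the result in the light of section 8 would expect much better precision than it has.

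**Working it through.** **Inputs.** From section 8: AUC 0.75 against 0.5, alpha 0.05, power 90%, 16 NR + 80 responders (R), n = 200, split 70:15:15, NR share 20%. From section 5: NR share 32%. The test cohort is 0.15 × 200 = 30, with 0.20 × 30 = 6 NR or 0.32 × 30 = 9.6, that is 9 or 10 NR.

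**Formulas (Hanley-McNeil).** For a true AUC of A with m NR and n R:

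- Q1 = A/(2 − A), Q2 = 2A²/(1 + A)
- SE² = [A(1 − A) + (m − 1)(Q1 − A²) + (n − 1)(Q2 − A²)] / (mn)
- Power = Φ((0.25 − z·SE0)/SE1), with SE0 at A = 0.5, SE1 at A = 0.75, and z = 1.96 two-sided or 1.645 one-sided.

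At A = 0.75, Q1 − A² = 0.6 − 0.5625 = 0.0375 and Q2 − A² = 0.6429 − 0.5625 = 0.0804. At A = 0.5 both differences are 0.0833.

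**The protocol's own figure.** The large-sample form of this calculation at five R per NR, two-sided 0.05 and 90% power gives 15.99 NR, hence 16 + 80 = 96. The finite-sample formula at 16/80 has SE0 = 0.0795 and SE1 = 0.0745, so power = Φ((0.25 − 0.1558)/0.0745) = 89.7%. One-sided power there would be 94.5%. The protocol does not state sidedness; two-sided is the reading that reproduces its number.

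**The test cohort of 30.**

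| NR / R | SE0 | SE1 | Two-sided power | One-sided power | Smallest significant AUC (two-sided) | 95% CI around 0.75 |
|---|---|---|---|---|---|---|
| 6 / 24 | 0.134 | 0.124 | 46.0% | 59.4% | 0.763 | 0.51-0.99 |
| 9 / 21 | 0.117 | 0.105 | 57.9% | 70.8% | 0.729 | 0.54-0.96 |
| 10 / 20 | 0.114 | 0.101 | 60.6% | 73.3% | 0.723 | 0.55-0.95 |

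For 6/24: Φ((0.25 − 1.96 × 0.134)/0.124) = Φ(−0.10) = 46.0%.

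**Check without the normal approximation.** Simulated binormal scores with an exact two-sided Mann-Whitney test gave 46.6% (6/24), 58.9% (9/21) and 63.1% (10/20).

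**How often the test cohort shows an AUC of 0.75 or more (binormal simulation, 40,000 runs).**

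| True AUC | 6 / 24 | 9 / 21 | 10 / 20 |
|---|---|---|---|
| 0.65 | 23.1% | 18.8% | 18.7% |
| 0.50 | 3.2% | 1.5% | 1.4% |

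**Size needed for 90% two-sided power.** About 84 test cases at 20% NR or 61 at 32% NR. At a 15% test share this means 84/0.15 = 560 or 61/0.15 = 407 cases in total.

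**The case against.** The strongest reply is that the protocol never assigns the 90% to the test cohort; it calls 96 a total and leaves it there. That is true, and the link is an inference. It rests on the goal being a final AUC and on the test cohort being the only place where the finished classifier is tested. If the 90% belongs to another analysis, section 8 does not say which.

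The sponsor also says openly that sample-size methods for such algorithms are unsettled, and treats the calculation as one of several approaches. This is fair, but the caveat does not touch the split, and the stated alpha, power and 96 still have to fit the design.

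It can also be said that the endpoint is development of a classifier, with no success rule tied to significance on the hold-out. This limits the consequence: nothing in the protocol turns on p < 0.05 in 30 cases. But the power statement itself presumes a test against 0.5, and the wide interval remains whether or not a test is done.

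Cross-validation is planned, and its details may properly sit in a statistical analysis plan that is not shown. The conflict here, however, is between two statements in the same protocol section, and cross-validation is given no role as the final test.

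One point stands as a limit on the concern. A classifier with no information would reach 0.75 in only about 1% to 3% of test cohorts, so false success by pure chance is not the main risk. The risks are missing a good classifier and mistaking a modest one for a good one.

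**Conclusion.** The concern holds. On the cases that carry the final test, the design gives about 46% (6 NR) to 61% (10 NR) two-sided power for a true AUC of 0.75, against the 90% aimed for in section 8. A classifier that meets the goal would be missed in about 39% to 54% of such studies instead of 10%. At 20% NR, an observed AUC exactly at the 0.75 goal falls just short of the critical value of 0.763.

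This assumes n = 200 is reached, the split is 140/30/30, and the NR share lies between the protocol's own 20% and 32%. The conclusion does not depend on sidedness, since one-sided power is 59% to 73%, and the exact test agrees with the approximation. The 16 in 96 is a share of 16.7%, not the stated 20%; that is a side issue and does not change the conclusion.

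**What to change.** **Required.** Restate the sample-size paragraph of section 8 so that the 90% cannot be read as applying to the 15% test cohort:

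- say that the 96 cases (16 NR) are cases entering the final AUC test, and that this figure rests on a 1:5 ratio;
- say whether alpha 0.05 is one- or two-sided;
- give the test cohort's actual power, about 46% to 61% two-sided;
- give the expected 95% interval around 0.75, about 0.51-0.99 at 20% NR and 0.55-0.95 at 32% NR.

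The cost is wording in one section, with no new patients or slides. The stated power becomes less favourable.

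**Optional.** As cross-validation is already planned, also report a nested cross-validated out-of-fold AUC with a 95% interval over all 200 cases, next to the locked hold-out result, with all method selection and tuning inside the inner loop. The expected interval is about 0.66-0.84 with 40 NR (SE 0.047) or 0.67-0.83 with 64 NR (SE 0.039), before fold-to-fold variance. This needs selection and tuning to be automated in every fold of the whole-slide pipeline, at extra computing cost. The resulting AUC describes the fitting procedure, not the single locked classifier, so the hold-out stays as planned.
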